## Abbreviations

Abbreviation	Term
CONSORT	Consolidated Standards of Reporting Trials
RCT	Randomised Controlled Trial
SPIRIT	Standard Protocol Items: Recommendations for Interventional Trials
WP	Work Package

## Executive summary

### Background

The deliverable D4.3 is part of Work Package 4: Development of protocol, ethics, questionnaires & piloting of data collection. This work package is closely linked to WP5, where the two-year stepped wedge cluster-randomised controlled trial of the EU PAL-COPD project is conducted, by developing the protocol that forms the foundation of the planning and conduct of the study.

### Objectives

The objective of the deliverable is to communicate key information regarding the design and conduct of the international stepped wedge cluster-randomised controlled trial. This study protocol presents the general framework of the trial; adaptations at the country level are possible for the purpose of meeting medical/research ethic committee requirements, but the core elements regarding design, eligibility criteria, study flow, outcomes, timing, and analysis as described below apply across all participating countries.

### Methodology and implementation

Writing of the protocol was guided by the 2013 Standard Protocol Items: Recommendations for Interventional Trials (SPIRIT) statement, also cross-referencing relevant points specifically for stepped wedge designs from the Consolidated Standards of Reporting Trials (CONSORT) extension. It received multiple rounds of feedback from all RCT partners (UGENT, ULANC, RUMC, UCPH, UPECS, UCP, KCL) who are responsible for carrying out the international trial and/or conducting data analysis for the trial. A first full draft was circulated in November of 2024, awaiting updates after pilot testing of the intervention. An updated version was created on April 1st, 2025 to enable RCT partners to prepare their submissions for ethics approval in a timely manner. Following partner feedback and revisions in June 2025, the latest version of the full protocol dates to 13 June 2025.

### Outcomes

The outcome of D4.3 presents a description of the core elements of the main study protocol, based on the full study protocol which has been shared with all RCT partners to enable applications to relevant medical and research ethics committees and review boards at the national and/or hospital level. It describes core aspects of the study including its aims and rationale, the study design, the study population and recruitment procedures, outcome measures and their timing, methods for the analyses of outcomes, and ethical aspects of the study.

### Impact

The main study protocol is a keystone in the project; guidance for conducting randomised trials emphasizes the importance of a comprehensive and robustly-designed protocol created a priori. The study protocol provides guidance for the procedures of the study which all scientific partners can refer to throughout the trial period, enables oversight by medical and research ethics committees, and specifies the aims of the study for which the collected data will be analysed.

### Next steps

During the preparation and execution of the trial, the study protocol will be the main reference for conduct of the study procedures regarding design, timing, outcomes, and statistical methods. The full length study protocol will be updated following the updated SPIRIT statement which was published in January of 2025, yielding a fully-detailed and comprehensive protocol for publication in a scientific journal. By publishing the protocol as an open-access scientific article, peer researchers, policy makers, clinicians and the public will be able to view a record of the study, to assess that the trial is conducted and analysed as prespecified. If amendments are proposed during the trial, the protocol will be

updated accordingly and submissions to medical/research ethics committees will be completed. A version history of the protocol will be kept.

## 1 Introduction

People with chronic obstructive pulmonary disease (COPD) experience significant symptom burden, leading to declining functional status and frequent hospitalizations in the advanced stages of the disease. This population often experiences unmet needs, including physical, emotional, social, and existential care needs. Exacerbations and hospitalisations for COPD are a risk factor for subsequent readmission; data collected from COPD admissions in 13 European countries shows that 35% of patients discharged for an exacerbation were readmitted within 90 days. This leaves patients vulnerable to rapid health deterioration after the first exacerbation and admission to hospital. Palliative care can improve the quality of life for patients with COPD by addressing needs across physical, psychological, social, or spiritual domains. However, people with COPD are an underserved population in this regard: although the palliative care needs of people with COPD could be as high as those of people with (lung) cancer, referral and access to (specialist) palliative care are limited in comparison.

A proactive approach to palliative care is needed, which integrates palliative care into routine care for COPD. Integrated palliative care actively involves the patient, family, and multidisciplinary clinical teams who are trained in the palliative care approach, ensuring continuity between all services involved. Early integration of palliative care is essential to reducing potentially preventable readmissions for patients with COPD.

The EU PAL-COPD project aims to achieve better quality of life and improved well-being for people with advanced COPD, by integrating palliative care into respiratory care via an innovative, non-pharmacological service-based intervention called ICLEAR-EU. The ICLEAR-EU intervention focuses on early identification of palliative care needs, multidisciplinary care integration including palliative, respiratory, and primary/community care, shared decision-making and advance care planning, and ongoing review of patient needs. The intervention is based on a model introduced in the United Kingdom (UK), where this multidisciplinary approach resulted in a reduction in hospital deaths.

From the UK-based intervention, the consortium adapted the intervention through consultation meetings with clinicians and patients/patient representatives in six countries (Belgium, the Netherlands, the United Kingdom, Denmark, Hungary, and Portugal), then pilot-tested the intervention internationally.

The present protocol concerns the large-scale international trial of the adapted and pilot-tested ICLEAR-EU intervention. In this study, patients with advanced COPD who are admitted to the hospital for more than 48 hours due to an acute exacerbation of their COPD, are invited to participate and will be followed up for 90 days.

### 1.1 Objectives

We aim to compare the ICLEAR-EU intervention to current usual care (treatment as usual) with regard to its:

1. Effectiveness in healthcare systems, as indicated by:

#### ***Primary Outcome Measure***

- a. The percentage of patients who have respiratory-related hospital readmissions within 90 days from baseline (or until death if before 90 days from baseline)

### ***Secondary Outcome Measures***

- b. **Patient outcomes:** illness perception, quality of life, mental wellbeing, existential wellbeing, presence of advance decisions to refuse treatment and documentation of advance care planning, preferred place of death
- c. **Caregiver outcomes:** quality of life, mental wellbeing, existential wellbeing, family carer burden, bereaved caregiver views of quality of care and death,
- d. **Healthcare utilisation outcomes:** Place of death, concordance between preferred and actual place of death, all-cause mortality, number of readmissions, length of hospital stays on readmission, referrals to specialist palliative care, ICU and emergency department admissions
- e. **Cost-effectiveness:** Cost per quality-adjusted life year (QALY)
- f. **Process and implementation evaluation:** We also aim to evaluate the **implementation processes** of the intervention: feasibility of integration into standard care, barriers and facilitators to implementation, and mechanisms involved in achieving outcomes in each participating country.

2. Effects on **subgroups**, including subgroups defined by characteristics known to affect health equity and equitable access:

- a. Comparison of outcomes **across participating countries**
- b. Effects on **subgroups** according to age, gender, socioeconomic status, cohabitation status, and hospital characteristics (e.g. urban vs. rural)

## **2 Methods**

### **2.1 Trial design**

We have chosen a stepped wedge cluster-randomized controlled trial design for this study, which is a pragmatic design that allows every participating hospital the opportunity to receive the intervention.

The stepped wedge cluster-randomized controlled trial will proceed in a similar fashion across the six countries (Belgium, the Netherlands, the United Kingdom, Denmark, Hungary, and Portugal). Clustering is at the level of hospital sites. Each country will include three hospitals. A schematic representation of the trial design is shown in Figure 1.

[figure not shown]

Figure 1. Stepped wedge design of the trial

Each hospital will go through four wedges, each wedge with a duration of six months, for a total of 24 months. Each hospital starts in control condition and crosses over to the intervention condition at 6, 12 or 18 months. The timing of cross-over will be randomly assigned at study onset. Before a hospital crosses over from the control condition to the intervention condition, a 30-day transition period will be integrated into the last control wedge, during which clinicians will receive the intervention training and implementation support will be provided.

## 2.2 Study setting

The intervention will be implemented in the hospital setting and will also involve community/primary care.

## 2.3 Eligibility criteria

**Hospitals:** Hospitals that typically admit 100–500 patients annually for COPD-related causes and indicate a willingness to implement ICLEAR-EU meetings will be included in the study. Hospital sites have in-patient respiratory beds.

**Patients and family caregivers:** Patients with advanced COPD living at home, who are admitted to the hospital for more than 48 hours because of an acute exacerbation of COPD and who will potentially benefit from an integrated palliative care approach, are eligible for participation. For data collection purposes, patients who are enrolled during a control wedge will not be re-enrolled for data collection in the intervention wedge.

Patients may also indicate a family caregiver for participation. We consider the family caregiver to be “any relative, friend, or partner who has a significant relationship and provides assistance (physical, social, and/or psychological)” to the patient. Not including a family caregiver does not exclude the patient from eligibility.

Inclusion and exclusion criteria for patients and family caregivers are described in Table 1.

Table 1. Patient and family caregiver inclusion and exclusion criteria

Patient	Family Caregiver
Inclusion criteria	

 
Have a diagnosis of advanced COPD*
 
Admission to the respiratory ward of the hospital that lasts <math>\geq</math> 48 hours (or likely to be admitted for <math>\geq</math> 48 hours) for an acute exacerbation
 
Live at home
 
	
 
Identified by the patient as the person who gives him or her the most help and support at home on a regular basis
 
Age 18 years or over
 

Exclusion criteria	

 
Currently receiving care from a formally recognised specialised palliative care team
 
Cognitive impairment preventing informed consent as judged by treating respiratory physician and by the researchers. In case of doubts, the researcher will consult the corresponding treating respiratory physician.
 
Not able to speak or understand the language in which measurements are conducted, these being: 
 
English
 
Dutch
 
Danish
 
Portuguese
 
Hungarian
 
 
 
Patients can be included in the study only once and cannot be re-enrolled during the overall duration study, even if at a different wedge.
 
	
 
Cognitive impairment preventing informed consent as judged by treating respiratory physician and by the researchers. In case of doubts, the researcher will consult the corresponding treating respiratory physician.
 
Not able to speak or understand the language in which measurements are conducted
 

#### \*Advanced COPD

1. Spirometry (FEV1):
  - a. Severe COPD:  $30\% \leq \text{FEV1} < 50\%$  predicted **OR**
  - b. Very severe COPD:  $\text{FEV1} < 30\%$  predicted

OR

2. High symptom burden:
  - a. Modified Medical Research Council (mMRC)  $> 2$  **OR**
  - b. COPD Assessment Test (CAT)  $> 20$

OR

3. High-risk exacerbation history:
  - a.  $\geq 1$  exacerbation leading to previous hospitalisation in the past year **OR**
  - b.  $\geq 1$  exacerbation leading to previous ICU admission in the past year

## 2.4 Participant timeline

The timeline for each patient (and family caregiver, if included) participant is shown in Figure 2. Participants fitting the eligibility criteria will be in the intervention or control condition, based on whether the hospital site is in a control or intervention wedge at the moment of the participant's informed consent and baseline assessment.

[figure not shown]

Figure 2. Participant timeline

## 2.5 Intervention and control

### 2.5.1 Control wedges

All sites start as control sites for 6 months. After the first 6 months, hospitals will cross over to the intervention at 6-monthly intervals (see Figure 1). During control wedges, sites will provide patients with treatment as usual according to the routine practice of each hospital, and in accordance with the practice of the healthcare system in each country.

### 2.5.2 Intervention wedges

During intervention wedges, the hospital sites will provide the ICLEAR-EU intervention. The developed Intervention Manual (Version 5, Post Pilot Clinical Manual; see Deliverable D2.6) contains the full intervention description, which will be provided for the clinicians delivering the intervention at the hospital sites.

The intervention consists of five core components supported by two implementation strategies, shown in Figure 3.

[figure not shown]

Figure 3. Overview of the ICLEAR-EU intervention

The five core components are:

1. **Identification** of unmet palliative care needs using assessment tools
2. **Communication** about goals of care and sharing with patient, family, and care team.
3. Shared decision-making regarding **Levels of Escalation**, contributing to a patient management plan for future care
4. Initiating **advance care planning** conversations with the patient and family (if present)
5. Ongoing **Review** and management of palliative care needs during follow-up visits with healthcare professionals, and revision of the patient management plan if or when necessary.

The implementation strategies consist of **training** for clinicians delivering the intervention, and overall **integration of palliative care** by improving inter- and multidisciplinary communication via shared reporting and outreach from hospital to community care. To achieve this, a weekly multidisciplinary ICLEAR-EU meeting will be implemented where the patients will be presented to discuss goals of care, levels of escalation and potential treatment plans. A form will be used to summarize the use of the intervention for each participant (the ICLEAR-EU form). The intervention is provided at the service level in each hospital. When hospitals are in the intervention wedge, they will apply the patient flow and deliver core components to patients with advanced COPD who are admitted for an exacerbation, as shown in Figure 4.

[figure not shown]

Figure 4. Diagram of pre-intervention steps and intervention procedures for hospitals in intervention condition

## 2.6 Measurement

### 2.6.1 Demographics

We will collect participant demographic data at baseline (T0), after completion of informed consent. Demographic characteristics collected can be found in Table 2 below.

### 2.6.2 Primary outcome

The primary outcome is the percentage of patients who have a respiratory-related readmission to the hospital within 90 days of baseline (or until death if within these 90 days). This is in line with outcomes reported in other studies across Europe, which will allow for comparison. We hypothesize that fewer people in the intervention phase will require hospital readmission.

### 2.6.3 Secondary outcomes

Secondary outcomes measured during the study are shown in Table 2 below, along with the timing for data collection.

Table 2. Constructs measured in the study, corresponding instruments, scheduling

Construct	Data collection measure	Completed by	Timing		
			T0 (Baseline)	T1 (30 days post-baseline)	T2 (90 days post-baseline)
Patient outcomes					
Demographics	

- Age

- Sex

- Marital status

- Children

- Cohabitation status

- Hours of transit to hospital where recent hospitalization occurred

- Highest level of education completed

- Employment status

- Comfort of living on household income

- Financial difficulties due to physical condition or treatment

- Country of birth + parent country of birth (if different from respondent birth country)

	Patient	x		
Perception of illness	Brief Illness Perception Questionnaire 	Patient	x	x	x

Quality of life	SF-CRQ   EQ-5D-5L   ICECAP-SCM 	Patient	x	x	x
Mental wellbeing	PHQ-4 	Patient	x	x	x
Existential wellbeing	MQOL-R existential subscale 	Patient	x	x	x
Preferred place of death + whether this has been discussed with health care professionals	Questionnaire item	Patient	x	x	x
Presence of advance decisions to refuse treatment (ADRTs) and advance care plans (ACPs)	ICLEAR-EU form and medical notes	Physician/researcher			x
[Bereaved] caregiver outcomes					
Demographics	
 
- Age
 
- Sex
 
- Marital status
 
- Children
 
- Cohabitation status
 
- Relationship to the person with COPD
 
- Living with the person with COPD
 
- Distance from home of person with COPD (hours)
 
- Highest level of education completed
 
- Employment status
 
- Comfort of living on household income
 
- Financial difficulties due to physical condition or treatment of family member with COPD
 
- Country of birth + parent country of birth (if different from respondent birth country)
 
	Caregiver	x		

Quality of Life	EQ-5D-5L 	Caregiver	x	x	x
Mental wellbeing	PHQ-4 	Caregiver	x	x	x
Existential wellbeing	MQOL-R existential subscale 	Caregiver	x	x	x
Family carer burden	ZBI-12 	Caregiver	x	x	x
Bereaved caregiver views of quality of care and death	VOICES-SF 	Bereaved caregiver	3 months post-bereavement		
Healthcare utilisation of enrolled patients					
Place of death	Medical notes or phone GP	Researcher	As appropriate		
Concordance between preferred place of death and actual place of death	Questionnaire item Medical notes or phone GP	Researcher	As appropriate		
All-cause mortality	Medical notes	Physician/researcher	As appropriate		
Number of readmissions to hospital	Medical notes	Physician/researcher			x
Median length of hospital stays on readmission	Medical notes	Physician/researcher			x
Number of referrals to specialist palliative care	ICLEAR-EU form and medical notes	Physician/researcher			x
Intensive Care Unit (ICU) admissions	Medical notes	Physician/researcher			x
Emergency Department admissions	Medical notes	Physician/researcher			x

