## 2.9.1 Masking/blinding

Hospitals are randomized according to their number (1, 2, or 3) only. However, participants and researchers cannot be fully blinded, as the intervention differs from treatment as usual and there is a training period for clinicians preceding the implementation.

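### Presence of advance decisions and advance care plans is scheduled at T2 only, with no baseline status or document date, so prior documents shrink the contrast and an imbalance in them could not be seen or adjusted for

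*Protocol*

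**What the plan says.** Section 1.1 of the protocol names the outcome as "presence of advance decisions to refuse treatment and documentation of advance care planning". Table 2 in section 2.6.3 repeats it as "Presence of advance decisions to refuse treatment (ADRTs) and advance care plans (ACPs", gives the source as "ICLEAR-EU form and medical notes", names the physician or researcher as the person completing it, and marks T2 (90 days) only.

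The nearest related item, "Preferred place of death + whether this has been discussed with health care professionals", is a patient questionnaire item taken at T0, T1 and T2.

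Neither section limits the outcome to documents made after baseline, asks for a document date, or excludes patients who already hold one. The related exclusion in section 2.3 is "Currently receiving care from a formally recognised specialised palliative care team". One route to eligibility in the definition of advanced COPD is an "exacerbation leading to previous hospitalisation in the past year".

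On recruitment, section 2.4 assigns condition by the wedge in force at consent. Section 2.8 has the respiratory team approach patients. Section 2.3 includes patients "who will potentially benefit from an integrated palliative care approach". Section 2.9 reveals the next hospital at months 4, 10 and 16, ahead of crossovers at 6, 12 and 18. Section 2.9.1 states that "participants and researchers cannot be fully blinded".

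**The concern.** Initiating advance care planning is one of the five core components in section 2.5.2, so this outcome lies close to what the intervention is meant to change. A single reading at day 90 scores a document written before the index admission the same as one written because of the intervention. Two things are at stake.

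- **Dilution.** Patients who already have a document are present at T2 in either condition, so they add nothing to the contrast and reduce power.
- **Imbalance.** If the share with prior documents differs between control and intervention recruits, the difference enters the estimate. The random hospital effect absorbs stable differences between hospitals and the time effect absorbs a secular trend. Neither removes a change in patient mix that coincides with crossover.

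Without prior status or a date, the analyst cannot check for imbalance or adjust for it.

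**Working it through.** The protocol gives no figure for this outcome, so there is none to reproduce. All rates below are assumptions.

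**1. Type of measure.** The other rows marked only at T2 (readmissions, length of stay on readmission, palliative care referrals, ICU and emergency department admissions) record events or stays during follow-up, for which extraction at T2 is natural. Presence of a document is a state that can begin before enrolment. Earlier documents are plausible because a hospitalisation in the past year is a route into the trial.

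**2. Model.** Let e0 and e1 be the shares with a prior document in control and intervention, and q0 and q1 the probabilities of a new document among the rest. Prevalence at T2 is P = e + (1 - e) × q, assuming that prior documents are still present at T2. Then

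P1 - P0 = (1 - e0) × (q1 - q0) + (e1 - e0) × (1 - q1).

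The first term is the diluted effect and the second is the imbalance.

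**3. Dilution** (e1 = e0 = e; assumed q0 = 20%, q1 = 50%, a 30-point effect):

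- e = 10%: 0.90 × 30 = 27 points
- e = 20%: 0.80 × 30 = 24 points
- e = 30%: 0.70 × 30 = 21 points
- e = 40%: 0.60 × 30 = 18 points

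**4. Imbalance**, (e1 - e0) × (1 - q1), for new-document rates of 10% to 50%:

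- 5 points: 5 × 0.50 = 2.5 up to 5 × 0.90 = 4.5
- 10 points: 10 × 0.50 = 5 up to 10 × 0.90 = 9

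The range is about 2.5 to 9 points. The sign follows the direction of the imbalance: at a 10% new-document rate and no true effect, 30% in control against 20% in intervention gives -9.

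**5. What this does to a test.** This uses the Hussey-Hughes variance with the design in section 2.7: 18 hospitals, four wedges, 17 × 0.7 = 11.9 analysed per hospital and wedge, two-sided 5%. The ICC of 0.05 is borrowed from the primary outcome. The assumed new-document rates are 10% and 30%.

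| Prior share | T2 control | T2 intervention | Difference | Odds ratio | Power |
|---|---|---|---|---|---|
| 0% | 10% | 30% | 20 | 3.86 | 99% |
| 10% | 19% | 37% | 18 | 2.50 | 93% |
| 20% | 28% | 44% | 16 | 2.02 | 82% |
| 30% | 37% | 51% | 14 | 1.77 | 68% |
| 40% | 46% | 58% | 12 | 1.62 | 54% |

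Only the decline matters here, since the absolute power depends on borrowed inputs.

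With no true effect and a 10% new-document rate in both conditions, prior shares of 20% control and 25% intervention give a 4.5-point difference and about a 13% chance of significance. With 20% and 30%, the figures are 9 points and about 38%. The nominal rate is 5%.

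**The case against.** **The row belongs with the chart data.** It is not patient-reported, so the T0, T1 and T2 schedule of the questionnaires is not its proper comparator, and the T2 mark may mean only when the notes are abstracted. This stands as a reading of the table. It does not supply a baseline value, because nothing on the page asks for a date or prior status.

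**Prevalence at T2 is a legitimate intention-to-treat quantity.** This stands. A reader might infer that prior documents bias the result; when balanced, they only make the contrast smaller. Nor does the protocol need to replace presence with newly made documents, which would be a different estimand.

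**Prior status may be recoverable.** A reader might infer that the problem is beyond repair. It is not: many documents will carry dates in notes that are opened anyway. The data retrieval form (section 2.10) and the full-length protocol are not shown and could contain such fields. What can be said is that this document does not require them.

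**The SAP can handle it.** Covariates and derivations do belong there, but a SAP can adjust only for what is collected. The Executive summary treats outcomes and timing as core elements that apply in all countries.

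**Selection is generic and unproven.** A reader might infer that recruitment will differ by condition, or that an imbalance passes almost whole into the estimate. The documents show only that the opportunity exists, and the pass-through is 50% to 90% on the rates used above. Whether place of death was discussed is asked at T0, which is a partial check but does not record these documents. Excluding patients under specialist palliative care may also lower the prior share.

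**Conclusion.** The point holds as a gap in the data schedule for one secondary outcome. The outcome is a state that may predate the admission, it is scheduled once at T2, and neither prior status nor date is requested.

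The dilution factor (1 - e) follows from the definition, given that prior documents persist to T2. Its size, 27 to 18 points from an assumed 30, rests on assumed prior shares of 10% to 40%. The imbalance effect of about 2.5 to 9 points is a possibility in either direction. It rests on an assumed imbalance of 5 to 10 points and new-document rates of 10% to 50%, none of which the protocol gives. Prevalence at T2 stays a valid target, and the primary analysis is unaffected.

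**What to change.** Add to the ADRT/ACP row of Table 2, and to the data retrieval form, two items: whether an ADRT or ACP dated before the index admission exists, and its date. Extract both from the medical notes in the same way in both conditions.

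In the analysis:

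- Keep presence at T2 as the outcome and adjust its logistic mixed model for baseline status.
- Report baseline status by condition, so that any imbalance is visible.
- Report documents newly made since the index admission as a supporting analysis, ascertained from the medical notes in both conditions. Section 2.5.2 describes the ICLEAR-EU form as a summary of the intervention's use, so it appears to exist only in intervention wedges and should not be the source for this comparison.

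Prior documents will nearly always still be present at T2, so the baseline coefficient may be very large or not estimable. The SAP should name a fallback, such as penalised estimation, or fitting the model among patients without a prior document and standardising the predicted risks to the whole sample.

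The cost is two fields from notes already opened, with no added visit or patient burden. Extraction takes slightly longer, and some documents will be undated and need a stated rule.
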